**Exclusion criteria:**

- 1) Alzheimer's Disease or other neurodegenerative disease such as Parkinson's Disease;
- 2) Current use or use in the past 3 months of antimicrobial or steroid drugs;
- 3) Medical conditions affecting immune status (e.g., heart failure, inflammatory bowel disease, hepatitis C, HIV);
- 4) International travel in the past 3 months.
- 5) Previous known side effect or negative reaction to VSL#3 or *Triphala*.

Note that heart failure, inflammatory bowel disease, hepatitis C, and HIV patients are excluded due to these diseases featuring variable and significantly altered immune status and gut microbiome, which are the main outcome measures of the study. This pilot study seeks to identify relatively healthy elderly subjects to assess these markers in the context of dietary supplementation.

**Assessment visits.** Assessment personnel will be naive to the participant group assignment. Testing will take place at SOM Building 4. At T1 (baseline): participants will 1) review their study responsibilities with the opportunity to reconsider participation 2) provide a stool and small blood sample for biomarker assessment; 3) complete psychosocial measurements via questionnaires; 4) receive group assignment instructions at the end of the visit. Measures will be repeated at T2 (post-intervention period).

**Randomization.** A computer-generated randomization algorithm will determine group assignment to ensure that participant demographics are evenly distributed across study conditions.

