#### **Statistical Issues**

Analytic Approach. Summary statistics (means, SDs, ranges, frequencies) will be computed for all variables of interest and compared between the treatment arms at baseline using 2-sample tests to test if randomization achieved balance in key covariates across groups. In the event of pre-existing variable group differences associated with dependent or relevant clinical variables, the nuisance variables will be statistically controlled. Outcome measures (e.g. health-related behaviors, psychological health, and objective measures of microbiome health and inflammation) will be transformed as needed to better approximate Gaussian distributions. The proposed study period is 2 months; hence we anticipate little loss-to-follow-up. However, subjects may drop out for a variety of reasons. It is important to take missing data into account when testing hypotheses of interest. Mixed-models can be applied even if some observations are missing as long as the data are "missing at random". Missing data (e.g., drop-outs) will be tested to determine if it is informative, and the methods to test for completely random dropouts will be applied. If needed, pattern-mixture models will be developed which take "missingness" into account when estimating parameters of interest using the methods of Park & Lee.

Analysis Plan. Two sample *t*-tests will be used to compare change scores (post-treatment minus pretreatment) in each outcome. Given the multiple outcomes, we will also use O'Brien's test which can be used to compare multiple endpoints across groups; we will apply O'Brien's test to the multiple outcomes for each hypothesis (e.g., psychological health via positive and negative affect, depressive symptoms; health behaviors via diet, physical activity, medication adherence, and alcohol usage). The O'Brien test statistic is a weighted linear combination of the *t*-statistics for each outcome. Finally, we will fit mixed effects models, with a subject-specific intercept included to allow for individual variability in outcome. Main covariate effects will be treatment group, time (pre-treatment and immediately post-treatment), and the group X time interaction. Likelihood ratio tests will be used to test the significance of these covariates. A significant group X time interaction will indicate that outcome trajectories differ across treatment groups.

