**11. RECRUITMENT AND PROCEDURES PREPARATORY TO RESEARCH**

**Overview.** A total of 75 participants who are generally healthy and otherwise meet our study criteria will be recruited and randomly assigned to either an 8-week synbiotic group, herb alone, or placebo control with a goal to obtain 60 patients who complete the study (20 in each group) after an estimated 20% attrition. Placebo control subjects will be given the option of having the 8-weeks of herbal synbiotic for directed personal use upon conclusion of the study. [name] has volunteered to help identify individuals who meet criteria for this study. Additional staff members responsible for assisting with recruitment are listed elsewhere in this application.

With this application, we are requesting a Waiver of Documented Consent to conduct the telephone screens. Asking interested individuals whether they meet the basic study criteria over the telephone (age, immune disorder diagnosis, medication use) presents no more than minimal risk of harm and involves no procedures for which written consent is normally required outside of the research context. Written consent will be obtained at the initial, in-person visit before any study questionnaires are administered or research procedures are performed.

With this application, we are also requesting a partial waiver of HIPAA authorization so that our study staff may help clinical staff identify potentially eligible participants using EPIC. When a member of our research team identifies a patient who may be eligible, he or she will then send a secure EPIC email asking the provider if they agree that a given patient is a good candidate for the study and asking the provider to speak with his or her patient about our study. The provider will provide a brief overview of the study during the patient's clinical

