### **14. POTENTIAL RISKS**

Participation in this study may involve some added risks or discomforts. These include:

- a. Pain, risk of fainting, lightheadedness and dizziness associated with the blood draw.
- c. Mild soreness and/or a bruise at the needle site.
- d. A small risk also exists that the vein may form a clot at the needle stick, which will gradually clear over one to two weeks.
- e. Risk of local infection at blood draw site.
- f. There is risk of loss of confidentiality. This will be minimized by using an identifier number rather than patient's name on all of the information gathered for the study.
- g. There may be mild psychological discomfort answering personal questions.
- h. There may be mild psychological discomfort providing a stool sample.
- i. There is an additional risk of bleeding for people taking blood thinning medications. Though considered to be a low risk, participants may want to discuss this with their physician prior to enrolling in the study.

Since this is an experimental treatment, there may be some unknown risks that are currently unforeseeable.

There are no known drug interactions or medical risks known with taking *Triphala*; a side effect of *Triphala* includes potential slightly looser bowel movement that is transient or resolves upon reduction of dose or cessation of *Triphala*. VSL#3 may cause a side effect of possible mild abdominal bloating in the first few days of consumption, which is a transitory phenomenon due to changing intestinal microflora that is self-resolving or can be reduced by decreasing the daily probiotic dose.

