## **Data Safety Monitoring Plan**

This is a low risk protocol. At the request of the IRB, the study investigators have appointed [name], Professor of Medicine, as the Data Safety Monitoring Officer (DSMO) who will help ensure adequate progress, patient's safety and confidentiality of personal information. [name] is not otherwise connected with the proposed project, however his research interests are similar to those included in the present study and he has been involved in similar types of studies. [name] will be in charge of evaluating and monitoring aspects of the study including participants' physical/medical safety, side effects and adverse events. [name] is familiar with the herbs, study operations, and data collection procedures found in the present study. The DSMO will monitor participants per the following:

1. Review and assessment of the performance of the study operations.
2. Examination of interim results of the study for evidence of efficacy or adverse effects.
3. Possible termination of the study because of early attainment of study objectives.
4. Identifying safety concerns or inadequate performance by staff.
5. Ensuring that any paper records, which reflect electronic data or relationships of those data, are kept in locked cabinets. Each PC workstation's operating system has a password protection scheme that allows startup of the system only by those with knowledge of the designated password.
6. The PIs will be charged with the reporting of all deaths and serious adverse events to both the DSMO and the IRB. This notification is submitted in writing to the IRB within 24 hours. Other adverse events will be reported within 10 working days.
7. Each participant's health status will be monitored and reported by the Project Coordinator to the Safety Monitoring Board on a monthly basis. Formal Safety Monitoring Board reports will be submitted to the IRB with each continuing review application during the active phase of the project.
8. Review any adverse events if any occur. PI will ask the Project Coordinator to break the code and have the statistician in our study determine if adverse events occur significantly more frequently in any one condition.

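### The adverse-event rule in the Data Safety Monitoring Plan breaks the code to the coordinator and the trial's own statistician, with no threshold, timing rule or firewall

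*Combined protocol and SAP*

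**What the plan says.** Item 8 of the Data Safety Monitoring Plan opens with "Review any adverse events if any occur". It continues: "PI will ask the Project Coordinator to break the code and have the statistician in our study determine if adverse events occur significantly more frequently"; the comparison is between conditions.

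Other parts of the combined protocol and SAP bear on this:

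- **Same plan, item 6** separates deaths and serious events from other adverse events for reporting. Item 8 makes no such distinction.
- **Same plan, item 7** has the Project Coordinator monitor each participant's health status and report it monthly.
- **Same plan, introduction** appoints a DSMO from outside the project to evaluate side effects and adverse events. Item 8 stands in the list of what the DSMO monitors, but the people it names for the code break are the PI, the coordinator and the study statistician.
- **Section 9, Assessment visits:** "Assessment personnel will be naive to the participant group assignment". No similar statement is made for the PI, the coordinator or the statistician.
- **Section 9, Statistical Issues:** outcomes "will be transformed as needed to better approximate Gaussian distributions". Covariate adjustment depends on baseline differences that are found, and pattern-mixture models are fitted only if judged necessary.
- **Section 14** lists minor expected effects, without frequencies: looser stools with Triphala, soreness or bruising from the blood draw, and "VSL#3 may cause a side effect of possible mild abdominal bloating in the first few days of consumption".

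**The concern.** Safety review sometimes needs unmasked data. The usual safeguard is to keep that knowledge away from the people who run and analyse the trial. Item 8 sends it to them.

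Two people matter most. The coordinator would know allocations while still collecting and reporting health status, which could affect which adverse events are noticed and recorded. The statistician would know allocations while transformations, nuisance covariates and the missing-data model are still open. Those choices apply to many outcomes, and the Sample Size and Power paragraph says that Type I error was not controlled across endpoints. A reader of the results could not rule out that knowledge of arm influenced the choices. Masking cannot be restored once it is lost.

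**Working it through.** **1. Who learns what.** The comparison is between conditions, so it cannot be made by unmasking only the participant who had the event. It needs the arm of every participant randomised up to that point. The text has the coordinator break the code and the statistician run the comparison, so these two see allocations. The PI asks for the break, but the text does not say that the PI receives the result by arm.

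**2. What filters the trigger.** Item 8 gives no filter for seriousness, severity, relatedness or a minimum count, and no date or interval for the comparison. It does not mention masked labels or a separate unmasked statistician.

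**3. Number of participants exposed to the rule.** The plan's recruitment figure reproduces: 60 completers / (1 − 0.20) = 75. An equal split over three groups gives 25 per arm.

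**4. Chance that the rule's condition is met at least once.** The documents give no adverse-event rate, so the per-person rate r is an assumption. With independent participants, P(at least one event) = 1 − (1 − r)^n.

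| Assumed r | n = 25 | n = 75 |
|---|---|---|
| 1% | 1 − 0.99^25 = 22% | 1 − 0.99^75 = 53% |
| 2% | 1 − 0.98^25 = 40% | 1 − 0.98^75 = 78% |
| 5% | 1 − 0.95^25 = 72% | 1 − 0.95^75 = 98% |
| 10% | 1 − 0.90^25 = 93% | 1 − 0.90^75 = 99.96% |

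The rate at which the chance over 75 participants reaches 95% is 1 − 0.05^(1/75) = 3.9%.

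**5. What a single event could show.** Take one event in one arm of 25 and none in the other 50. The two-sided Fisher exact p is 25/75 = 0.33. On the same comparison, two events against none give p = 0.108 and three against none give p = 0.034, unadjusted for three arms or repeated looks. A code break after the first event would therefore give up masking and could not answer the question item 8 asks.

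**The case against.** **The timing is not stated, and a frequency test presupposes accumulated events.** This stands. A reader might infer that the first event triggers the break. Item 8 does not say so, and a periodic or end-of-study comparison fits the text as well. What remains is that the plan does not say which is meant.

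**Loss of the blind is not shown to be almost certain or early.** This stands too. At 1% to 2%, the chance of any event is 22% to 40% after 25 participants and 53% to 78% after 75. Whether a needle bruise or mild bloating counts as an adverse event is also undefined. The chance is near certainty only at about 5% or more. Given the minor effects in Section 14 and the absence of a filter, that is plausible, but it is an assumption.

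**Item 8 does not contradict the masking of assessors.** Correct. Only assessment personnel are expressly masked. For the coordinator and statistician, masking is implied only by there being a code to break, and the coordinator may already have access to it. That makes a firewall more necessary, but it does not create a contradiction.

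**The effect on outcomes is limited.** This partly stands. The microbiome and blood markers are laboratory measures, and the questionnaires are completed by participants, whom item 8 does not unmask. The statistician's open choices apply to all of these outcomes.

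**Two further inferences are not supported.**

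- A reader might call item 8 a weak safety screen. With 25 v 25, 5 events against 0 give p = 0.0502, and power for 20% v 4% is 23%. With one arm against the other two (25 v 50), the same five events give p = 0.003, and power is 55%. The plan names no test, so neither figure can be held against it. The DSMO's review and items 4, 6 and 7 are also in place.
- A reader might see a second leak in Section 11, where placebo participants are "given the option of having the 8-weeks of herbal synbiotic for directed personal use upon conclusion of the study". That reveals allocation early only if the phrase means each participant's own last visit, which is not its natural reading.

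**Conclusion.** The concern holds as a gap in procedure. For any adverse events, item 8 gives allocation to the coordinator and the trial's own statistician with no threshold, timing rule or firewall, although an independent DSMO is already appointed. If the comparison is made during the trial, it unmasks both while health reporting continues and analysis choices remain open.

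The chance that at least one event occurs among 75 participants runs from 53% at an assumed 1% rate to over 99.9% at 10%. These figures assume independent participants and rates that the documents do not supply. They give the chance that the rule's condition is met, not the chance that the code is in fact broken early. The documents do not support saying that the blind is bound to be lost early or that the PI will see allocations.

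The change should be made because it is cheap and loss of masking is irreversible. For a small pilot, it is not a condition for the trial to be worth running.

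**What to change.** Rewrite item 8 along these lines: adverse events are tabulated by masked arm label (X/Y/Z) and reported to the DSMO, who alone may request the key. The PI, Project Coordinator, assessment staff and trial statistician are not given arm identities until database lock, apart from individual emergency unmasking, which is logged. State when the tables are produced, for example with the monthly health report that item 7 already requires. Item 2 already has the DSMO examine interim results, so the role does not change in kind.

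The cost is a wording amendment, with two small downsides. The PI sees arm-level safety data only through the DSMO. Someone outside outcome assessment and analysis must hold the label key and prepare the tables; the protocol describes a randomisation algorithm but names no such person. The amendment should be in place before enrolment.

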Sample Size and Power. We hypothesized a Cohen's *d* effect-size (standardized mean difference between groups) of 0.75 based on previous studies. With at least 60 subjects completing 2 visits, we will have 80% power (2-sided alpha=0.05) to detect a 0.75 effect-size (Cohen's *d*). To be conservative, we aim to recruit 75 subjects to this study, allowing for a 20% drop-out/loss-to-follow-up rate and a total of 60 subjects completing the 2 visits. Note that our calculations did not control the Type I error for the multiple endpoints. Our objective in this small pilot study is to obtain early evidence of the putative efficacy of this novel intervention on a multitude of outcomes, psychosocial and biological, in the elderly. We expect our findings to inform the design of a larger future clinical trial in elderly subjects.

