#### **10. HUMAN SUBJECTS**

This project will recruit 75 and test a total of 60 healthy elderly subjects from UCSD ADRC. We aim to test 60 participants (20 per group, 3 groups) from UCSD.

Patients who are elderly and cognitively intact will be identified, screened, and recruited from UCSD ADRC following the procedures outlined in Section 11 below.

Study testing visits will take place at SOM Building 4.

Along with the referring physician, [name] will oversee determination of whether potential subjects fit eligibility criteria according to the criteria outlined below.

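### The monitoring plan's only stated between-arm adverse-event comparison is an unspecified significance test, which at about 25 per arm often misses moderate harms; report event counts and risk differences by arm instead

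*Combined protocol and SAP*

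**What the plan says.** The Data Safety Monitoring Plan, in section 15, lists eight tasks. Item 8 provides for review of any adverse events. The code is then broken and the study statistician is to "determine if adverse events occur significantly more frequently" in any one arm. No test, significance level, sidedness, unit of analysis (events or participants), estimate or interval is given, and no consequence is attached to either result.

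The analysis plan under Statistical Issues does not mention adverse events. The only power statement concerns a standardised mean difference: "we will have 80% power (2-sided alpha=0.05) to detect a 0.75 effect-size". The same section adds: "Note that our calculations did not control the Type I error for the multiple endpoints".

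On numbers, Statistical Issues says "we aim to recruit 75 subjects to this study, allowing for a 20% drop-out/loss-to-follow-up rate". Section 10 says "We aim to test 60 participants (20 per group, 3 groups) from UCSD", and section 11 gives the same target: "with a goal to obtain 60 patients who complete the study (20 in each group) after an estimated 20% attrition".

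Other items in the monitoring plan bear on safety without reference to a test. The safety officer examines interim results for adverse effects (item 2) and identifies safety concerns (item 4). Deaths, serious events and other adverse events are reported (item 6), and health status is reported monthly (item 7).

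**The concern.** Item 8 is the only place where the documents say how adverse events will be compared between arms, and the criterion it gives is statistical significance. Nothing in the sample-size reasoning shows what difference in event rates such a criterion could detect. In a trial this small it may often return a non-significant result when one arm does have moderately more events, and the plan asks for no estimate that would show how large a difference remains compatible with the data.

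The side effects that section 14 expects, looser stools and bloating, can also occur without the products, so a comparison of rates with placebo is what would show an excess. The trial is meant to inform a larger one in older people. For that purpose an estimate with its uncertainty is useful, and a bare statement of non-significance is not.

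**Working it through.** **Inputs.** From the documents: 60 completers, 20 per group, three groups, 20% dropout, 75 recruited. Assumed: an equal split of the 75, alpha of 0.05 for safety (the plan gives that level for efficacy only), participants as the unit, and the true event rates.

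**The plan's own figure.** 60 / (1 − 0.20) = 75, which reproduces. 75 / 3 = 25 per arm.

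**One table under several tests.** Take 5/25 v 0/25.
- One-sided Fisher: C(25,5) / C(50,5) = 53,130 / 2,118,760 = 0.025.
- Two-sided Fisher: twice that, p = 0.0502.
- Uncorrected chi-square: 50 × (5×25 − 20×0)² / (25×25×5×45) = 5.56, p = 0.018. With Yates correction, p = 0.059.
- One arm against the other two pooled, 5/25 v 0/50: C(25,5) / C(75,5) = 53,130 / 17,259,390, p = 0.003.
- At 20 per arm, 5 v 0 by two-sided Fisher: p = 0.047.

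So the plan's wording does not settle whether 5 v 0 counts as a signal.

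**Chance of a significant result.** For true rates p₁ (higher arm) and p₀, sum Bin(a; n₁, p₁) × Bin(b; n₂, p₀) over all tables (a, b) whose p-value is at most 0.05.

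| Assumed true rates | Two-sided Fisher, 25 v 25 | One-sided Fisher, 25 v 25 | Uncorrected chi-square, 25 v 25 | Two-sided Fisher, 25 v 50 pooled |
|---|---|---|---|---|
| 20% v 5% | 20% | 33% | 38% | 46% |
| 30% v 10% | 31% | 45% | 45% | 51% |
| 25% v 5% | 37% | 52% | 56% | 64% |
| 20% v 0% | 38% | 58% | 77% | 90% |
| 30% v 0% | 81% | 91% | 97% | 99% |
| 50% v 10% | 83% | 91% | 91% | 96% |

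The pooled column assumes that both other arms share the lower rate. With one-sided Fisher or chi-square in place of two-sided Fisher, the pooled figure for 20% v 5% rises to about 50% or 51%. At the 20 completers per arm, pairwise detection of 20% v 5% is 17% (two-sided Fisher) to 29% (chi-square).

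**When pooling does not help.** Two arms receive Triphala. If both carried the harm, with 5, 5 and 0 events, either Triphala arm against the other two (5/25 v 5/50) gives two-sided Fisher p = 0.29. A three-arm exact test on the same counts gives 0.040.

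**Size that would be needed.** For 80% power at 20% v 5%, the mean rate is 0.125, and n per arm = [1.96 × √(2 × 0.125 × 0.875) + 0.842 × √(0.20 × 0.80 + 0.05 × 0.95)]² / 0.15² = (0.917 + 0.383)² / 0.0225 ≈ 75.1. That is 76 per arm, or 88 with continuity correction.

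**What estimation gives.** For 5/25 v 0/25 the risk difference is 20 points. The Wilson limits are 8.9% to 39.1% and 0% to 13.3%. The Newcombe interval therefore runs from 20 − √(11.1² + 13.3²) = 2.6 points to 20 + 19.1 = 39.1 points.

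**The case against.** The strongest reply is that significance is not the gate for a safety concern. The safety officer's reviews under items 2 and 4, the event reporting under item 6 and the monthly reports under item 7 all proceed whatever the p-value, and item 8 itself starts with a review of the events. This stands. A reader might infer from item 8 that a non-significant result would be taken as proof of safety, but the plan never says so and attaches no action to the test. What remains is that none of those other items specifies a comparison of rates between arms.

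A second reply is that the size of the problem depends on a test the plan does not name. This also stands in part. A reader might take it as fact that 5 v 0 would not be significant. That holds by two-sided Fisher, by a margin of 0.0002, and by Yates-corrected chi-square, but not by one-sided Fisher, uncorrected chi-square or one arm against two pooled. The word for more frequent is directional, and the reference to any one condition makes the pooled reading natural.

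Third, a reader might infer that real harms would usually go unflagged whichever arms are compared. The table does not support that. Large differences are usually detected, and pooled detection of 25% v 5% is 64%.

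Finally, it is fair to say that this is a small pilot with low-risk products and that the event rates used here are invented. They are assumptions, and a different background rate would move the figures.

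**Conclusion.** The point holds in a limited form. A significance criterion with no test, alpha, sidedness or estimate is a weak basis for the only stated between-arm adverse-event comparison. At about 25 per arm, an assumed 20% v 5% is flagged in 20% to 38% of trials pairwise and about 46% pooled by two-sided Fisher. An assumed 30% v 10% is flagged in 31% to 45% pairwise and 51% pooled. So moderate harms are missed in roughly half of trials or more, while differences as large as 30% v 0% would usually be seen.

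This rests on an equal split of the 75, a 0.05 level and the assumed rates. It does not show that the trial is unsafe, that oversight depends on a p-value, or that the investigators would read non-significance as equal safety. It shows that the planned comparison says little about moderate differences and that the same counts could be called significant or not according to a choice the plan leaves open.

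**What to change.** In item 8, replace the determination of significance with a table for the safety officer. For each arm it gives the number and percentage of participants with each type of event, together with risk differences between arms and their 95% confidence intervals. State that the safety officer judges these irrespective of any p-value, and that a non-significant difference is not evidence of equal safety.

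The cost is one sentence in the monitoring plan and one extra table, with no new data or staff. The downside is that there is no longer a formal yes-or-no test result. The intervals will be wide, as the 2.6 to 39.1 points for 5/25 v 0/25 shows, but that width is the information a later trial needs.
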